8.4 Withdrawal of individual subjects

Subjects can leave the study at any time for any reason if they wish to do so without any consequences. The investigator can decide to withdraw a subject from the study for urgent medical reasons.

8.4.1 Specific criteria for withdrawal (if applicable)

Not applicable.

8.5 Replacement of individual subjects after withdrawal

Subjects will only be replaced in case the first visit (i.e., the first, full assessment procedure with Aurisvue) was not completed for purposes that were unrelated to the performance or the characteristics of Aurisvue.

8.6 Follow-up of subjects withdrawn from treatment

Not applicable.

8.7 Premature termination of the study

The study will be terminated in case the performance of the device is insufficient to warrant further inclusion or follow-up of study subjects or if regulatory requirements are no longer met (e.g., if the manufacturer cannot support the study any longer because it stops pursuing the use of OCT technology for middle ear problems).

9. SAFETY REPORTING

9.1 Temporary halt for reasons of subject safety

In accordance to section 10, subsection 4, of the WMO, the sponsor will suspend the study if there is sufficient ground that continuation of the study will jeopardise the patient's health or safety. The sponsor will notify the accredited METC without undue delay of a temporary halt including the reason for such an action. The study will be suspended pending a further positive decision by the accredited METC. The investigator will take care that all subjects are kept informed.

9.2 AEs, SAEs and SUSARs

9.2.1 Adverse events (AEs)

Adverse events are defined as any undesirable experience occurring to a subject during the study, whether or not considered related to the investigational medical device. All adverse events reported spontaneously by the subject or observed by the investigator or his staff will be reported by the investigator to the Sponsor by filling out the corresponding eCRF. The Sponsor will record all AEs, based on NCI CTCAE reporting standards¹³.

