3. STUDY DESIGN

This study is an observational study. No treatment intervention for study purposes is included and all patients will receive routine clinical care. The study is intended to explore the feasibility and possibilities of OCT for structural and functional imaging of the middle ear.

The duration of the study will be approximately one year. Patients will be recruited from those visiting the Department of Otorhinolaryngology and Head and Neck Surgery, Erasmus Medical Center, Rotterdam, the Netherlands.

Patients included in the study will be imaged at least once with Aurisvue. If a patient returns to the site within the duration of the study and relevant physiological or pathological changes to the middle ear are expected (due to, for example, treatment or the natural history of the disease), the patient may be imaged again. Except for assessment with Aurisvue, no study related procedures are prescribed, and patients will receive the usual standard of care.

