8.1.2 Secondary study parameters/endpoints (if applicable)

- Number of middle ear structures (TM, ossicles) on which OCT-vibrometry measurements by Aurisvue succeeded.
- For diagnostic correlation with other clinical data sources (only as far as they are available from the standard of care):
 - o microscopic otoscopy (description)
 - o CT-scan
 - o MRI-scan
 - o pure-tone audiogram
 - o tympanogram
 - o surgical report (if available)
- Number of AEs and SAEs
- PREMs

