10.2 Secondary study parameter(s)

Answering the first secondary objective ('To assess the feasibility of functional OCT imaging with Aurisvue in clinically relevant subjects with middle ear problems') will be done in the same way as described above for the primary objective, albeit based on functional OCT-vibrometry measurements using a sound stimulus rather than the structural OCT images.

For the second secondary objective ('To assess the clinical potential of structural and functional OCT imaging with Aurisvue in clinically relevant subjects with middle ear problems'), the data obtained by Aurisvue will be (qualitatively) correlated with other clinical data sources. Similarities (such as Aurisvue image information consistent with other imaging modalities) and dissimilarities (such as characteristics visible on Aurisvue images but not on another imaging modality) will be evaluated.

AEs, SAEs and questionnaires will be included in answering the primary and both secondary objectives. Again, missing data will be reported and not imputed.

Patient reported experience measures (PREMs) will be recorded immediately after the measurements with Aurisvue are completed.

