13.2 Synthesis

There are three main potential sources of risk for patients: optical power, acoustical power and malfunction of the integrated camera.

- The intensity of the OCT beam is below the maximum permissible exposure level for continuous illumination of tissue. Aurisvue employs two scanners for lateral imaging. Typical imaging duration is a few minutes. The probability of harm due to optical power is therefore improbable. The severity of the harm is moderate (CTCAE grade 2). The risk related to optical power is deemed to be insignificant (and thus acceptable).
- Likewise, the sound used to induce movement of the TM and ossicular chain for OCT-V measurements is well below the hazardous threshold, even when used continuously. The probability of harm directly due to acoustic power is therefore improbable. The severity of this harm is moderate (CTCAE grade 2). This risk directly related to acoustic power is deemed to be insignificant (and thus acceptable).

In addition, there is an indirect risk related to unexpected exposure to an acoustical stimulus, which may cause a patient to suddenly move his head. The probability of harm due to sudden movement of the patient's head caused by unexpected acoustical exposure is improbable. The severity of this harm is severe (CTCAE grade 3). The risk

related to this sudden movement is deemed to be acceptable. It is addressed in the Aurisvue's instructions for use and will be addressed during training.

- Malfunctioning of the integrated camera limits the feedback to the operator with respect to the location of the device and may therefore result in inadvertent contact of the speculum with the tympanic membrane. The probability of harm due to a malfunctioning camera is improbable. The severity of this harm is severe (CTCAE grade 3). The risk related to a malfunctioning camera is deemed to be acceptable. It is addressed in the Aurisvue's instructions for use and will be addressed during training.

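### Adverse events are counted only if volunteered or observed, and no item counts device malfunctions without harm or missing data, so the AE count could understate mild events.

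*Combined protocol and SAP*

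**What the plan says.** **How AEs are found.** Section 9.2.1 gives the capture rule: "All adverse events reported spontaneously by the subject or observed by the investigator" or staff go to the sponsor on the eCRF. The definition is broad: "Adverse events are defined as any undesirable experience occurring to a subject during the study", related to the device or not. No start or end of AE collection is set for the individual patient.

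**Contacts.** Section 3 states: "Patients included in the study will be imaged at least once with Aurisvue". If a patient returns and a change in the middle ear is expected, "the patient may be imaged again". Beyond the Aurisvue assessment, the protocol prescribes no study procedure.

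**What patients are asked.** Section 8.3 has one experience question, comparing Aurisvue with regular or microscopic otoscopy. Under 10.2 it "will be recorded immediately after the measurements with Aurisvue are completed".

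**Use of the count.** "Number of AEs and SAEs" is a secondary parameter in 8.1.2. Section 10.2 uses AEs, SAEs and questionnaires for the primary and both secondary objectives.

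**Malfunctions.** Section 13.2 lists three main sources of risk. On the third it says: "Malfunctioning of the integrated camera limits the feedback to the operator". The possible result is speculum contact with the tympanic membrane, with harm rated CTCAE grade 3 and its probability rated improbable. Section 10.1 reports missing OCT data with reasons. No item in 8.1.2 or section 9 covers a malfunction that neither harms the patient nor loses data.

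**The concern.** A count of AEs can only be read against the method that produced it. Here a symptom enters the data if the patient brings it up or if someone sees it. Brief discomfort, dizziness or tinnitus are hard to see and easy for a patient not to mention, so they are the events most likely to be lost.

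The malfunction gap is separate. If the camera view drops out briefly, the operator recovers and the scan is usable, the patient has had no undesirable experience and no OCT data are missing. The event falls outside both the AE definition and the missing-data listing. Yet it is the precursor of a hazard that the protocol itself names, in a prototype that 11.5 describes as not CE-marked.

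At stake is how a low or zero AE count may be interpreted when the results are used for further development and future trials, as section 1 intends. The early-termination rule in 8.7 also refers to insufficient device performance without naming a measure. A malfunction count would inform it.

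**Working it through.** The protocol states no expected AE rate, no target precision and no alpha, so there is no planned figure to reproduce. The arithmetic below only illustrates how incomplete capture changes the reading of a clean count.

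**Inputs**
- n = 100, the maximum number of patients (4.4).
- x = 0 patients with a recorded AE: a scenario chosen for illustration.
- s = probability that a patient with an AE has it recorded. The documents give no value. The range 0.8 to 0.3 is an assumption, and s = 1 is complete capture.

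**Step 1: bound with complete capture.** The exact upper limit for 0 of n is 1 − α^(1/n).
- One-sided 95%: 1 − 0.05^(1/100) = 0.0295, or 2.95%.
- Two-sided 95% (Clopper-Pearson): 1 − 0.025^(1/100) = 0.0362, or 3.6%.

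**Step 2: bound with incomplete capture.** If the true rate is p, the recorded rate is p·s. Setting (1 − p·s)^n = α gives p = [1 − α^(1/n)] / s.

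| s (assumed) | One-sided 95% | Two-sided 95% |
|---|---|---|
| 1.0 | 2.95% | 3.6% |
| 0.8 | 2.95% / 0.8 = 3.7% | 3.62% / 0.8 = 4.5% |
| 0.3 | 2.95% / 0.3 = 9.8% | 3.62% / 0.3 = 12.1% |

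**Step 3: chance of a clean count at a given true rate**, (1 − p·s)^100.
- p = 3%: 0.97^100 = 4.8% at s = 1; 0.991^100 = 40.5% at s = 0.3.
- p = 5%: 0.95^100 = 0.6% at s = 1; 0.985^100 = 22.1% at s = 0.3.

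**Step 4: where each kind of event would be recorded**

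| Event | Recorded under |
|---|---|
| Visible event during imaging | AE, by staff observation (9.2.1) |
| Symptom the patient mentions | AE, by spontaneous report (9.2.1) |
| Symptom neither mentioned nor seen | No route in the protocol |
| Malfunction that prevents a scan | Reason for missing data (10.1) |
| Malfunction that harms the patient | AE or SAE (9.2) |
| Malfunction with no harm and a usable scan | No item in 8.1.2 or section 9 |

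The third and last rows are the gap.

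**The case against.** The strongest reply is that this is an exploratory observational study whose risk is classed as negligible (12.2), and that its capture rule is adequate for it. Five parts of that reply deserve an answer.

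- **Staff observation.** A reader might infer that capture rests on spontaneous reports alone. It does not. Operator and patient are together throughout a handheld examination of about 10 minutes, so sudden head movement or speculum contact should be seen. This stands, and it confines the gap to mild, subjective or delayed symptoms.
- **The experience question.** It may draw out discomfort. But it asks for a comparison with otoscopy and is not an AE enquiry.
- **Period of reporting.** A reader might infer that AEs are collected at one visit only. The definition covers the whole study, repeat imaging is allowed, known AEs are followed to resolution or stability and SAEs are reported to the end of the study (9.4). The documents do not say how many patients are seen once. Still, follow-up of known AEs does not find unreported ones, and no later study contact is required.
- **Other routes for malfunctions.** A reader might infer that malfunctions without harm go unrecorded. That cannot be established: the IMDD, the instructions for use and the eCRF are not in this file. The annual progress report includes other problems (12.4), but that is not a count per examination. What can be said is that 8.1.2 and section 9 have no such item.
- **Value of the extra data.** Zero malfunctions in 100 examinations would still allow a rate of about 3%, so the count cannot confirm a rating of improbable. It could contradict one. Solicited symptoms will also partly reflect the disease, since section 1 itself links cholesteatoma with vertigo and hearing loss, and there is no comparator. This is a reason to report solicited events separately, not a reason not to ask.

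**Conclusion.** The concern holds in a limited form. AE capture is unsolicited and no contact after imaging is required, so mild or subjective symptoms could be undercounted in a figure that feeds every objective. The protocol also lacks an item for malfunctions without harm or missing data, despite naming camera malfunction as a main source of risk.

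The numerical size depends wholly on an unknown capture rate. Over the assumed range of 80% to 30%, a clean count in 100 patients supports a one-sided bound of 3.7% to 9.8% instead of 2.95%. With fewer than 100 patients every bound is wider. A completely clean count may itself be unlikely, because the AE definition is so broad; the same undercounting applies to a low non-zero count.

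A reader might go further and conclude that the study will overstate the safety of the device. The documents do not support that. The objectives in section 2 are feasibility and clinical potential, no safety conclusion is planned, and the extent of any undercount is unknown. The point is a minor improvement, not a flaw in the primary analysis.

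**What to change.** 1. **Sections 8.3 and 9.2.1.** Ask every patient one standard open, non-leading AE question at the end of each Aurisvue session, next to the experience question. Tie it to the session and not to routine ENT visits: only some patients return, so asking there would make capture uneven across patients and conditions.
2. **Section 10.2.** Report solicited AEs separately from spontaneous or observed ones. Give the number of patients with at least one AE, with an exact confidence interval on the number of patients examined. State that symptoms arising after the session still depend on the patient reporting them.
3. **Section 8.1.2 and the eCRF.** Add the number of device malfunctions per examination, including loss of camera view, whether or not harm or missing data resulted. State whether an examination means a session or an ear, since both ears are imaged.

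**Cost.** Two eCRF items and under a minute per session, with no extra visit. More mild events will be recorded, some of them caused by the underlying ear disease, and the report should say so.

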9.2.2 Serious adverse events (SAEs)

A serious adverse event is any untoward medical occurrence or effect that

- results in death,
- is life-threatening (at the time of the event),
- requires hospitalisation or prolongation of existing inpatients' hospitalisation,
- results in persistent or significant disability or incapacity,
- is a congenital anomaly or birth defect; or
- any other important medical event that did not result in any of the outcomes listed above due to medical or surgical intervention but could have been based upon appropriate judgement by the investigator

An elective hospital admission will not be considered as a serious adverse event.

The investigator will report all SAEs that may be related to the Aurisvue device or Aurisvue operating procedures to the sponsor and the manufacturer without undue delay after obtaining knowledge of the events, except for the following SAEs: None

The sponsor will report these SAEs through the web portal *ToetsingOnline* to the accredited METC that approved the protocol, within 7 days of first knowledge for SAEs that result in

death or are life threatening followed by a period of maximum of 8 days to complete the initial preliminary report. All other SAEs will be reported within a period of maximum 15 days after the sponsor has first knowledge of the serious adverse events.

9.2.3 Suspected unexpected serious adverse reactions (SUSARs)

Not applicable (no investigational medicinal product).

9.3 Annual safety report

Not applicable (no investigational medicinal product).

9.4 Follow-up of adverse events

All AEs will be followed until they have abated or until a stable situation has been reached.

Depending on the event, follow up may require additional tests or medical procedures as indicated, and/or referral to the general physician or a medical specialist.

SAEs need to be reported till end of study within the Netherlands, as defined in the protocol.

9.5 Data Safety Monitoring Board (DSMB) / Safety Committee

Not applicable.

10. STATISTICAL ANALYSIS

10.1 Primary study parameter(s)

The presence of a discernible TM and the number of discernible ossicles on structural OCT imaging will be reported by descriptive statistics. This will be the primary source of information for the primary objective of this study: To assess the feasibility of structural OCT imaging with Aurisvue in clinically relevant subjects with middle ear problems.

Because the occurrence of missing data (e.g., no OCT was acquired) is of interest for the primary objective of this study, no imputation will be performed. Instead, missing data will be reported as such, including the reasons of such missing data.

10.2 Secondary study parameter(s)

Answering the first secondary objective ('To assess the feasibility of functional OCT imaging with Aurisvue in clinically relevant subjects with middle ear problems') will be done in the same way as described above for the primary objective, albeit based on functional OCT-vibrometry measurements using a sound stimulus rather than the structural OCT images.

For the second secondary objective ('To assess the clinical potential of structural and functional OCT imaging with Aurisvue in clinically relevant subjects with middle ear problems'), the data obtained by Aurisvue will be (qualitatively) correlated with other clinical data sources. Similarities (such as Aurisvue image information consistent with other imaging modalities) and dissimilarities (such as characteristics visible on Aurisvue images but not on another imaging modality) will be evaluated.

AEs, SAEs and questionnaires will be included in answering the primary and both secondary objectives. Again, missing data will be reported and not imputed.

Patient reported experience measures (PREMs) will be recorded immediately after the measurements with Aurisvue are completed.

10.3 Other study parameters

All other study parameters may be used to stratify the data used to answer the primary and secondary objectives. Again, because no power calculation was performed, no definite conclusions may be drawn from this analysis, but it may be used to produce new hypotheses for future testing.

10.4 Interim analysis (if applicable)

Not applicable.

11. ETHICAL CONSIDERATIONS

11.1 Regulation statement

This study will be conducted in accordance with the principles of the Declaration of Helsinki (October, 2013), the Medical Research Involving Human Subjects Act (WMO; July 1, 2021), the Guidelines for Good Clinical Practice E6(R2) (EMA/CHMP/ICH/135/1995, Dec 1, 2016) and the EU Medical Device Regulations (2017/745).

11.2 Recruitment and consent

Patients scheduled for a visit at the ENT-department will be screened based on the available information (medical records and/or referral information). Prospective participants will be informed by the otolaryngologist at their visit and are provided with additional information by letter (brochure) that they take home. The researcher contacts the participant at least 2 days later by phone and, when the patient decides to participate, schedules the appointment for a research visit. During the research visit, any questions regarding the study can be answered and the participant will be asked to provide written informed consent for the study. Costs for travelling and parking will be reimbursed.

11.3 Objection by minors or incapacitated subjects (if applicable)

Not applicable.

11.4 Benefits and risks assessment, group relatedness

Subjects do not benefit from participation. The risk is minimal (see chapter 5 of the IMDD for the full risk assessment and benefit-risk analysis). The burden of participation is low: the assessment with Aurisvue is expected to take approximately 10 minutes of extra time during a study visit.

11.5 Compensation for injury

The sponsor and investigator have a liability insurance which is in accordance with article 7 of the WMO.

The sponsor (also) has an insurance which is in accordance with the legal requirements in the Netherlands (Article 7 WMO). This insurance provides cover for damage to research subjects through injury or death caused by the study.

The insurance applies to the damage that becomes apparent during the study or within 4 years after the end of the study.

In addition, the manufacturer of the Aurisvue has a product liability insurance that covers the product liability of the non-CE-marked Aurisvue within the scope of this clinical investigation.

11.6 Incentives (if applicable)

Not applicable.

12. ADMINISTRATIVE ASPECTS, MONITORING AND PUBLICATION

12.1 Handling and storage of data and documents

Access to patient information is restricted to members of the study team and to legitimate authorities only. No identifiable data on participants will be stored within the context of this study, except for the informed consent forms and the enrolment log. All data will be pseudonymized: data will be encoded by a patient code that is specific for this study and is unrelated to the clinical patient ID. The key to the patient code is available only to the investigator and the site's study team. All data will be stripped from identifiable information by the site prior to submitting such data to the study systems.

All data will be entered into an electronic data capture system (Castor EDC). Larger data points, such as large (three-dimensional) images or videos, will be pseudonymized and uploaded in the same system.

Processing of the data and presentation of the results of this study will be strictly anonymous. An export of the data stored in the EDC system will be shared with Acoustic Insight, the manufacturer of the Aurisvue, according to the provisions of the collaboration agreement and as specified in the patient information file.

12.2 Monitoring and Quality Assurance

Based on the NFU risk table (see Annex 2 of NFU Richtlijn Kwaliteitsborging Mensgebonden Onderzoek, December 2020), the following risks were estimated:

For patients: Negligible

For research data: Negligible

Overall: Negligible

Monitoring will be done by personnel that is not part of the Investigator's study team and will be performed in accordance with Annex 3 of the beforementioned NFU Guideline (column 'Verwaarloosbaar risico: Geneesmiddelen-, Medische hulpmiddelen Voedingsonderzoek').

